#### **8.9.2. Lost to Follow Up**

A participant will be considered lost to follow-up if he or she repeatedly fails to return for scheduled visits and is unable to be contacted by the study site.

The following actions must be taken if a participant fails to return to the clinic for a required study visit:

- The site must attempt to contact the participant and reschedule the missed visit as soon as possible and counsel the participant on the importance of maintaining the assigned visit schedule and ascertain whether or not the participant wishes to and/or should continue in the study;
- Before a participant is deemed lost to follow up, the investigator or designee must make every effort to regain contact with the participant (where possible, 3 telephone calls and, if necessary, a certified letter to the participant's last known mailing address or local equivalent methods). These contact attempts should be documented in the participant's medical record;
- Should the participant continue to be unreachable, he/she will be considered to be lost to follow up and exited from the study;
- When a subject is lost to follow-up, the reason for the early exit will be clearly documented on the appropriate eCRF.

## 8.10. Procedures for Unmasking of Study Medication

When necessary for the safety and proper treatment of the subject, the investigator can unmask the subject's treatment assignment to determine which treatment has been assigned and institute appropriate follow-up care. When possible, Whitecap Biosciences (or designee) should be notified prior to unmasking study medication. The investigator should inform Whitecap Biosciences (or designee) of the unmasking if there is no notification prior to the unmasking.

The treatment assignment for the subject can be determined by designated site personnel through the IWRS via password protected access. The reason for breaking the code must be recorded in the subject's source documents. [REDACTED]

## 9. Statistical Procedures

One database lock will occur when all subjects (both Part 1 and Part 2) have either completed the study or discontinued from the study prematurely, and all data queries have been resolved. Randomization release will occur following the database lock. A detailed statistical analysis plan (SAP) will be approved prior to database lock.

### 9.1. Analysis Population(s)

Each population will be analyzed based on the treatment received.

Part 1: The Safety population consisting of all treated subjects will be used for all analyses.

Part 2: The following populations will be used for analysis:

- The Safety population will consist of all treated subjects. All safety analyses will be performed using the safety population;
- The Modified Intent-to-treat (mITT) will consist of all randomized and treated subjects who provide IOP data at baseline and at least one post-baseline IOP assessment. This population will be used for analyses of efficacy data;
- The Per-protocol (PP) population is a subset of the mITT population and will consist of subjects who did not have any major protocol violations deemed to have potential impact on the primary endpoint. This population will be used to confirm the primary efficacy analysis and will be determined prior to database lock.

## 9.2. Sample Size Calculation

For each cohort in Part 1 of the study a sample size of 6 patients will provide 83% power to detect a 3 mmHg within-group change from pre-dose assuming a standard deviation of 2 and two-sided alpha = 0.05, based on a one-sample t-test. With larger standard deviations ( $\geq 2.5$ ) the power to detect this difference is <66%.

For Part 2, a sample size of 24 has > 90% power to detect a within-group mean changes from baseline IOP of 3 mm Hg, assuming a SD of 2.5 mm Hg. Also, power calculations were performed for the comparison of each dose of AGN-227535 versus Timolol. These calculations consider treatment differences (AGN-227535 minus Timolol) mean changes from baseline in study eye IOP in the mITT population at Day 14/Exit.

The power to detect treatment group differences from -1 to -4 mm Hg with common standard deviations (SDs) ranging from 2.5 to 3.5, based on a two-sample t-test are shown in Table 6.

**Table 6 Power Calculations for Study Part 2 Tests of Treatment Differences**  
(AGN-227535  $N = 24$ ; Timolol  $N = 12$ ; alpha = 0.05)

Treatment Group Difference	Common SD	Power (%)
-4	2.5	99
	3	96
	3.5	88
-3	2.5	91
	3	78
	3.5	65
-2	2.5	59
	3	45
	3.5	35
-1	$\geq 2.0$	<20

Additional sample size calculations were performed for tests of non-inferiority of either dose of AGN-227535 to Timolol. These calculations considered a non-inferiority margin of 1.5 mm Hg and one-sided  $\alpha = 0.025$ . With a treatment group difference of -1 mm Hg, the power ranged from 50% for a common SD of 3.5 to 78% for a common SD of 2.5.

The calculation was based on the non-inferiority tests for the difference between two means using t-test as implemented in the commercial software PASS version 16.0.3 (2018).

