### Clinical Hypotheses:

Parts 1/2: AGN-227535 has an acceptable safety and tolerability profile;

Part 1: The safety profile allows for assessing AGN-227535 in Part 2;

Part 2: At least 1 concentration of AGN-227535 demonstrates an IOP lowering effect.

**Type of Study:** Two-part, multi-centered [(Part 1- single-dose in one eye, open-labeled, dose-escalation), (Part 2 - multiple-dose, randomized, double-masked, active-controlled)], bilateral treatment.

**Study Population:** Adult (at least 18 years of age) male or female subjects with primary open-angle glaucoma or ocular hypertension in each eye who are otherwise in generally good health. Only one eye must meet all ocular entry criteria.

**Number of Subjects and Sites:** Approximately 100 subjects will be screened to participate in the study (Part 1 – 25; Part 2 – 75). An expected 95 subjects will be assigned to study treatment such that approximately 18 (Part 1) and 60 (Part 2) subjects complete the study at 3-5 sites. Subjects who do not complete the study may be replaced.

Part 1: Approximately 6 subjects per dose-escalation cohort (up to 3).

Part 2: Up to 2 investigational doses will be chosen based on results from Part 1.

Approximately 24 subjects per AGN-227535 group and approximately 12 subjects for the timolol group will be given study treatment.

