### **3. Study Design and Rationale**

**Study Design Description:** This is a 2-part study designed to evaluate the safety, tolerability and IOP-lowering effects of AGN-227535 in subjects with primary open-angle glaucoma (POAG) or ocular hypertension (OHT). Approximately 100 subjects are planned to be enrolled at up to approximately 5 study centers in the United States.

In Part 1, an open-label dose-escalation of AGN-227535 0.05%, 0.15% and 0.4% is planned in order to assess initial safety, tolerability and IOP-lowering effects. Approximately 6 subjects will be exposed to a single dose (to one eye) at each concentration level. Between

cohorts, all available data will be used to assess the appropriateness to pursue the next concentration. Approximately 25 subjects will be screened so that 18 subjects complete the study.

In Part 2, In addition to the primary analysis of the within-group mean IOP change from baseline, a parallel comparison of AGN-227535 with timolol 0.5% is planned. Study treatments will be administered twice-daily for 14 days. Up to 2 investigational doses will be chosen based on results from Part 1. Subjects will be randomized in a 2(:2):1 ratio to receive one of up to two concentrations of AGN-227535 (based on results from Part 1) or timolol ophthalmic solution 0.5% and will be stratified based on IOP at Baseline, Hour 0 ( $\leq$  25 mm Hg versus  $>$  25 mm Hg). Approximately 24 subjects per AGN-227535 group and 12 subjects for the timolol group will be given study treatment. If 2 investigational doses are selected: approximately 75 subjects will be screened so that 60 subjects complete the study.

For both Parts 1 and 2, potential subjects will be screened within the 50 days prior to initiation of treatment. Thus, the total duration of study participation for each subject is up to 2.5 months which includes 4 (Part 1) and 5 (Part 2) in-clinic visits. The visit schedule requires day-long visits at some time points to perform sufficient clinical assessments. The primary efficacy endpoint (Part 2) is IOP change from baseline at each time-matched hour at Day 14/Exit.

Subject safety will be monitored throughout the study.

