#### **9.3.1 Efficacy (Part 2)**

##### **9.3.1.1 Primary Efficacy Endpoint(s)**

The primary response measure is IOP. Two consecutive measurements of IOP will be taken for each eye, with the right eye measured first. If the first two measurements of either eye differ by more than two mm Hg, a third measurement will be taken for the eye. Depending on the number of measurements required and obtained, the IOP for a given eye will be represented by either the average or the median of the readings. Details will be provided in the SAP.

The change from baseline for each eye at each post-baseline assessment is calculated as the IOP at that assessment minus the IOP at the corresponding hour at baseline. Efficacy will be evaluated in the study eye. The study eye is the eye that meets the inclusion/exclusion criteria. If both eyes meet the criteria, the study eye will be the eye with the worse (highest) IOP at Day -1 Hour 0. If both eyes have the same IOP value at this timepoint, the right eye will be the study eye.

The primary efficacy endpoints are the Day 14/Exit mean IOP changes from Baseline (Day -1) at each time-matched hour (0, 2, 4, 8). The primary hypothesis is that AGN-227535 ophthalmic solution effectively lowers IOP. The primary efficacy analysis is the within-

group mean change from baseline at Hour 2, the time of peak efficacy of timolol. This study will also assess if AGN-227535 is non-inferior to Timolol ophthalmic solution 0.5% with respect to change from baseline (follow-up minus baseline) in study eye IOP at each time-matched hour evaluated (hours 0, 2 4, and 8) at Day 14/Exit in the mITT population. The analyses will be performed via analysis of covariance (ANCOVA) which will have treatment as the main effect and the Baseline hour-matched IOP as the covariate in the model.

Pairwise treatment group comparisons will be performed for each individual dose of AGN-227535 versus timolol ophthalmic solution 0.5%. A 2-sided 95% confidence interval (CI) for the treatment difference (AGN-227535 Ophthalmic Solution minus Timolol ophthalmic solution 0.5%) will be constructed based on this ANOVA model for each AGN-227535 dose.

If AGN-227535 ophthalmic solution is determined to be non-inferior to Timolol ophthalmic solution 0.5%, a further attempt to show superiority of AGN-227535 over Timolol will be made.

Primary efficacy will be evaluated in the mITT population.

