**Table 8      Glossary of Definitions**

Term	Definition
End of Study	The date of the last visit of the last subject in the study
Subject Status	Subject status is defined below:
Study entry	A subject who has signed informed consent and has undergone at least 1 screening procedure and been entered into ITRS
In screening	A subject who has is undergoing the screening process and has not yet qualified for study enrollment.
Screen failure	Subject who has signed informed consent, has undergone at least 1 screening procedure, but fails to qualify for study at any time prior to and up until the completion of the Baseline visit.
Enrolled	A subject who qualifies for study based on Inclusion and exclusion criteria (Parts 1 and 2) (see Sections 4.1 and 4.2) AND is randomized (assigned a randomization number (Part 2).
Subject completion	A subject who has completed all phases of the study including the last scheduled procedure as shown in the Schedule of Visits and Procedures.
“Should” vs “Must”	Use of the word “should” means that it is suggested or recommended, but not required, whereas the use of the word “must” means that it is required.
Concurrent Medication	A medication that the study subject is taking at the time of enrollment or after
Concurrent Treatment	A procedure or other non-medication medical treatment that the study subject is receiving at the time of enrollment or after.
eg,	for example
ie,	in other words
Prior Medication	A medication taken by the study subject within time period specified in entry criteria prior to enrolling in the study. Other prior medications within 3 months prior to enrolling into the study.
Prior Treatment	A procedure or other non-medication medical treatment received by the study subject within time period specified in entry criteria prior to enrolling in the study. Other prior treatments within 3 months prior to enrolling into the study.
Study eye	The designated eye for use in analysis of IOP effects will be based on the eye with the higher IOP at Day -1, Hour 0. If both eyes qualify, the eye with the higher IOP at Baseline (Day -1) Hour 0 will be the study eye. If both eyes have the same IOP value at this timepoint, the right eye will be the study eye.

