## 3 STUDY DESIGN

This is a 2-part study designed to evaluate the safety, tolerability and IOP-lowering effects of AGN-227535 in subjects with primary open-angle glaucoma (POAG) or ocular hypertension (OHT). Approximately 100 subjects are planned to be enrolled at up to approximately 5 study centers in the United States.

In Part 1, an open-label dose-escalation of AGN-227535 [REDACTED] is planned in order to assess initial safety, tolerability and IOP-lowering effects. Approximately 6 subjects will be exposed to a single dose (to one eye) at each concentration level. Between cohorts, all available data will be used to assess the appropriateness to pursue the next concentration. Approximately 25 subjects will be screened so that 18 subjects complete the study.

In Part 2, in addition to the primary analysis of the within-group mean IOP change from baseline, a parallel comparison of AGN-227535 with timolol 0.5% is planned. Study treatments will be administered twice-daily for 14 days. Up to 2 investigational doses will be chosen based on results from Part 1. Subjects will be randomized in a 2(:2):1 ratio to receive one of up to two concentrations of AGN-227535 (based on results from Part 1) or timolol ophthalmic solution 0.5% and will be stratified based on IOP at Baseline, Hour 0 ( $\leq$  25 mm Hg versus  $>$  25 mm Hg). Approximately 24 subjects per AGN-227535 group and 12 subjects for the timolol group will be given study treatment. If 2 investigational doses are selected: approximately 75 subjects will be screened so that 60 subjects complete the study.

For both Parts 1 and 2, potential subjects will be screened within the 50 days prior to initiation of treatment. Thus, the total duration of study participation for each subject is up to 2.5 months which includes 4 (Part 1) and 6 (Part 2) in-clinic visits. The visit schedule requires day-long visits at some time points to perform sufficient clinical assessments. The primary efficacy endpoint (Part 2) is IOP change from baseline at each time-matched hour at Day 14/Exit.

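### The last row of the Part 2 power table is wrong at its stated SD bound (28.0% at SD 2.0, not below 20%), and the synopsis count of 95 assigned does not match group sizes that sum to about 78

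*Protocol*

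**What the plan says.** **Power table.** Protocol 9.2 introduces Table 6 as giving power for differences of -1 to -4 mm Hg with "common standard deviations (SDs) ranging from 2.5 to 3.5, based on a two-sample t-test are shown in Table 6". The table's subtitle fixes 24 subjects on AGN-227535, 12 on timolol and alpha 0.05. Protocol 9.3 makes treatment comparisons two-sided at 0.05. The last row pairs a difference of -1 mm Hg with an SD of at least 2.0 and a power of <20%. SAP 3.1 repeats the table with the same SD bound but prints ≤20%.

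Below the table, both documents give non-inferiority power for a 1.5 mm Hg margin, one-sided alpha 0.025 and a true difference of -1 mm Hg: "the power ranged from 50% for a common SD of 3.5 to 78% for a common SD of 2.5".

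**Counts.** The synopsis (Number of Subjects and Sites) has about 100 subjects screened, 25 for Part 1 and 75 for Part 2. It then says: "An expected 95 subjects will be assigned to study treatment such that approximately 18 (Part 1) and 60 (Part 2) subjects complete the study". Part 1 has about 6 subjects in each of up to three cohorts. For Part 2, Protocol 3 says: "Approximately 24 subjects per AGN-227535 group and 12 subjects for the timolol group will be given study treatment". Subjects who do not complete may be replaced, but no replacement number or dropout rate is stated.

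Protocol 3 says "Approximately 100 subjects are planned to be enrolled", and SAP 3 says the same: "Approximately 100 subjects are planned to be enrolled at up to approximately 5 study centers". Protocol Table 8 defines an enrolled subject as "A subject who qualifies for study based on Inclusion and exclusion criteria (Parts 1 and 2") and, for Part 2, is also randomized.

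**The concern.** A power statement with an open-ended SD bound should hold at the bound, where power is highest. Here it does not, and the bound lies outside the SD range that the text announces. Anyone reading the row literally would understate power at SD 2.0 by at least 8 percentage points (28.0 - 20). The two documents also disagree on the inequality sign.

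The count problem is one of traceability. A reader cannot tell whether the plan is to treat about 78 or about 95 subjects, or whether 100 is the number screened or the number who qualified. Recruitment, drug supply, the disposition table and the consent form's statement of approximate study size all rest on these figures.

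**Working it through.** **Inputs.** Group sizes 24 and 12, and alpha 0.05 (Table 6 subtitle); two-sided comparisons (Protocol 9.3); two-sample t-test with a common SD (Protocol 9.2).

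**Formula.** The standard error is SD × √(1/24 + 1/12) = SD × √0.125 = 0.3536 × SD. The noncentrality is |difference| / standard error, with 24 + 12 - 2 = 34 degrees of freedom. Power is the probability that a noncentral t variable falls beyond the two-sided 5% critical values.

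**Step 1: reproduce the plan's other figures.**

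| Difference (mm Hg) | SD | Stated power (%) | Recomputed (%) |
|---|---|---|---|
| -4 | 2.5 / 3 / 3.5 | 99 / 96 / 88 | 99.3 / 95.6 / 88.1 |
| -3 | 2.5 / 3 / 3.5 | 91 / 78 / 65 | 90.9 / 78.5 / 65.4 |
| -2 | 2.5 / 3 / 3.5 | 59 / 45 / 35 | 59.4 / 44.9 / 34.9 |

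All nine agree to within half a point, so the method is the plan's own. For non-inferiority, the distance from the assumed difference to the margin is 1.5 - (-1) = 2.5 mm Hg. One-sided alpha 0.025 then gives 78.5% at SD 2.5 and 50.1% at SD 3.5, against 78% and 50% stated.

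**Step 2: the last row, difference -1 mm Hg.**

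| SD | Standard error | Noncentrality | Power (%) |
|---|---|---|---|
| 2.0 | 0.707 | 1.414 | 28.0 |
| 2.25 | 0.795 | 1.257 | 23.1 |
| 2.5 | 0.884 | 1.131 | 19.6 |
| 3.0 | 1.061 | 0.943 | 15.0 |
| 3.5 | 1.237 | 0.808 | 12.3 |

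Solving for 20% power gives SD 2.47. Between SD 2.0 and 2.47 both the <20% and the ≤20% statements are false; from 2.5 upward both are true.

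**Step 3: could another convention rescue the row?** At SD 2.0 the alternatives give:
- normal approximation: 29.3%;
- one-sided 0.05: 39.8%;
- 12 versus 12: 21.6%;
- 24 versus 24: 39.6%;
- two-sided 0.025: 19.0%.

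Only the last is below 20%, and it is not the table's stated alpha.

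**Step 4: counts.** At the maximum design, Part 1 has 3 × 6 = 18 treated and Part 2 has 24 + 24 + 12 = 60, so 18 + 60 = 78 in all. That is also the number expected to complete. Against 95 assigned the difference is 95 - 78 = 17, or 17/95 = 18% of those assigned. Even if all 25 subjects screened for Part 1 were assigned, Part 2 would need 95 - 25 = 70 assigned, against 60 treated.

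**Step 5: the primary analysis.** A one-sample t-test with n = 24, a change of 3 mm Hg and SD 2.5 has more than 99.9% power, consistent with the stated >90%.

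**The case against.** **The row is a label slip with no consequence.** Within the announced SD range of 2.5 to 3.5 the row is right, its message of low power at 1 mm Hg holds even at 28%, and no sample size depends on it. All of that stands, and it is why the point is minor. A reader might infer that the whole table or the sample size is unsound; nine reproduced cells show otherwise.

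**The counts are approximate, and 78 is not a stated figure.** It is a sum that assumes three cohorts and two doses. Replacement is a stated mechanism by which assigned can exceed completing. Exclusion criterion 27 bars only earlier randomization in Part 2, so a Part 1 subject may enter Part 2, and the Amendment 4 summary says such a subject is counted once. It would therefore be too strong to say that 17 subjects are unaccounted for. What remains is that replacement can link 95 assigned to 78 completing, but not to groups sized at about 78 treated. No allowance is quantified, and overlap between the parts would lower the number of distinct subjects, not raise it.

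**Non-inferiority.** A reader might also infer that the non-inferiority decision is undefined, since the step "If AGN-227535 ophthalmic solution is determined to be non-inferior to Timolol ophthalmic solution 0.5%, a further attempt to show superiority" names no hour, and that the 50% to 78% power is therefore misleading. The documents do not support that. Protocol 9.3.1.1 and SAP 9.1 assess non-inferiority at each listed hour, with a confidence interval for each dose. SAP 9.1 labels this exploratory, both documents waive multiplicity adjustment, and the 1.5 mm Hg margin is prespecified in Protocol 9.2 and SAP 3.1. The power figures are correct per comparison. Making one hour the only non-inferiority test would change the plan, not correct it.

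**Conclusion.** The last row of Protocol Table 6 and of its SAP 3.1 copy is wrong as written. Power at SD 2.0 is 28.0%, not below 20%, and the claim becomes true only above SD 2.47. This rests on the table's own group sizes, alpha and test. That 2.0 was typed for 2.5 is an inference from the SD range in the text, not something the documents say.

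Secondarily, 95 assigned in the synopsis is not reconciled with treated groups summing to about 78 at the maximum design. Fewer cohorts or a single dose would widen that difference. The word enrolled is applied to 100 subjects whom the synopsis calls screened, contrary to Table 8.

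Severity is minor. No other cell, no group size and no conclusion about the primary within-group analysis at Day 14 Hour 2 changes.

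**What to change.** 1. Protocol Table 6 and the SAP 3.1 table, last row: change the SD bound from ≥2.0 to ≥2.5, and print the same sign (<20) in both.
2. Synopsis, Protocol 3 and SAP 3: give one screened, one treated and one completing number for each part. State the replacement allowance behind any excess of assigned over completing, and say how a subject who takes part in both parts is counted.
3. Use enrolled only as Table 8 defines it, and describe the 100 as screened if that is what is meant.
4. Optional, for readability: repeat the 1.5 mm Hg margin in Protocol 9.3.1.1 and SAP 9.1, and say there that non-inferiority is judged per dose and per hour.

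The cost is text and table edits in two documents, with no extra subjects and no new analyses.

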### **9.3. Methods of Analyses**

In general, data will be summarized with descriptive statistics which will include sample size, mean, standard deviation, median, minimum and maximum for continuous variables and frequency and percentage for categorical variables.

Part 1: All safety and IOP-lowering effects tabulations will provide descriptive statistics by cohort.

Part 2: For continuous variables, treatment groups will be compared using analysis of variance covariance techniques or two-sample t-tests. Nominal variables will be analyzed using Pearson's chi-square test or Fisher's exact test.

Analyses performed for the mITT population will use the method of last observation carried forward (LOCF) to impute missing values. No imputation for missing data will be performed for the PP or safety populations.

As this is an exploratory trial, all treatment comparisons will be made at the two-sided  $\alpha = 0.05$  level without adjustment for multiple comparisons.

